3.3. Disposition and baseline characteristics

Disposition of subjects and baseline characteristics will be described overall and by starting dose level, if applicable, to assess their comparability.

3.3.1. Disposition of subjects

Subject disposition will be tabulated for all subjects by summarizing the number and percentage of subjects completed study treatment, discontinued from the study and by the primary reason for discontinuation, who are included in the SAS overall and by starting dose level, if applicable.

A listing will present dates of study discontinuation and the primary reason, if applicable for each subject.

3.3.2. Protocol deviations

Important protocol deviations will be summarized in the overall SAS and by starting dose level if applicable, using the number and percentage of subjects who had each type of deviation for the SAS. COVID-19 related protocol deviation will be also summarized. Protocol deviations will be reviewed by the sponsor prior to the database lock. In addition, these protocol deviations will be listed:

- Inclusion/Exclusion criteria not respected
- Study Withdrawal criteria not respected
- Safety/Rights affected

3.3.3. Demographic data and other baseline characteristics

Demographic and baseline measurements will be summarized for the SAS, using standard descriptive summaries or categorical summaries, as appropriate. In addition to the summary tables, a listing will be provided for all demographic and baseline characteristics data.

In addition, listing of medical history will be provided. For this purpose, data of the CL2-95014-002 study may be used.

The following baseline characteristics will be summarized based on descriptive statistics:

- Age at inclusion (years; if not available, then it will be calculated as the biggest integer $\leq [(ICF\ date - date\ of\ birth + 1) / 365.25]$)
 - As continuous variable
 - By Age Category I (age <10, 10 - <16, and ≥ 16 years)
 - By Age Category II, EudraCT categories (0-27 days, 27 days-23 months, 2-11 years, 12-17 years, 18-65 years, ≥ 66 years)
- Sex
- Race
- Ethnicity
- Height (cm)
- Weight (kg)
- Body Mass Index (BMI (kg/m²) = weight (kg) / height (m²))
- Body Surface Area (BSA(m²) = sqrt (height (cm) x weight (kg) / 3600))

3.4. Treatments of subjects

3.4.1. Extent of exposure

The SAS will be used for exposure unless otherwise specified. Exposure to S95014 lyophilizate for each subject will be listed. The following metrics will be summarized:

- Duration of treatment (months): (last date of study drug – first date of study drug + 1) / 30.4375
- Number of doses administered: total number of S95014 infusions
- Cumulative actual dose (U/m²): total dose of study drug infused to a patient in the study
- Actual dose intensity (ADI, U/(m² × month)): cumulative actual dose (U/m²) / duration of treatment (months)

- Planned dose intensity (PDI, $U/(m^2 \times \text{month})$): cumulative planned dose (U/m^2) / duration of treatment (months), where cumulative planned dose = planned number of S95014 infusions \times starting dose
- Relative dose intensity (RDI): $ADI (U/m^2 \times \text{month}) / PDI (U/(m^2 \times \text{month}))$

Listing of all dose change/interruption and reasons will be produced.

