6.2. IMP dispensing

Patients will receive lyophilized S95014 every two weeks during the consolidation phase at the dose of 1000, 2000 or 2500 U/m², as per investigator's judgment.

At the withdrawal visit of the study, the investigator will propose a treatment adapted to the nature of the clinical state of the patient and according to his/her therapeutic group as defined in ALL-MB 2015 protocol (maintenance phase).

IMP will be dispensed by the pharmacist/responsible of the healthcare establishment upon prescription of the investigator only.

The investigator may only use the IMP provided for the patients involved in the study and treated under his/her responsibility or that of a designated co-investigator.

For each patient, the IMP will only be dispensed during the study.

Further instructions for the preparation and dispensation of S95014 are described in the Pharmacy Manual.

All dosages of S95014 prescribed to the patient and all dose changes during the study must be recorded in the eCRF.

The detachable portion of the label on the IMP box must be stuck by the investigator on an IMP label collection form or on the prescription form where the IMP are dispensed by a pharmacist.

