2.2. Investigational Medicinal Product (IMP) and dose level

S95014 lyophilizate is considered as IMP.

S95014 dosage is calculated according to body surface area (BSA). The BSA will be manually calculated by the investigator based on the height and weight measured on the day of S95014 infusion (all BSA calculations are rounded to 2 decimal places).

S95014 lyophilizate will be administered IV, over 1 to 2 hours, every two weeks during the consolidation phase at the dose of 1000, 2000 or 2500 U/m², as per investigator's judgment. Patients will be administered 9 infusions of S95014 lyophilizate, at week 7, 9, 11, 15, 17, 19, 23, 25 and 27. Patients will receive other backbone chemotherapy agents as per ALL-MB 2015 protocol.

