3.1.1. Descriptive statistics

For **qualitative data**, number of observed values, number and percentage of subjects per class will be presented. Unless otherwise specified in the TLG, no class "Missing" is considered.

For **quantitative data**, number of observed values, mean, standard deviation, median, first and third quartiles, minimum and maximum will be presented.

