3.5.1. Adverse Events

A treatment-emergent adverse event (TEAE) is defined as any untoward medical occurrence in a subject who received IMP (S95014), which occurs within the period from the Inclusion visit, until 30 days after the last S95014 infusion, or the date of withdrawal, whichever is earlier. TEAE will be assessed according to the National Cancer Institute (NCI) Common Terminology Criteria Adverse Events (CTCAE) v5.0. Clinically significant laboratory abnormalities will be classified into Common Terminology Criteria (CTC) grade according to CTCAE v5.0 and will be reported as adverse events if they are associated with signs and symptoms or, clinically significant in the investigator's opinion except if related to the disease, if they require curative therapies, if they induce change of study treatment administration. All analyses described below will be based on TEAEs, if not otherwise specified.

Adverse events will be summarized in hierarchical tables, presenting the number and percentage of subjects having at least one AE, and having at least one AE in each primary system organ class and for each preferred term using MedDRA coding. AEs will be sorted by descending frequency, and alphabetically where frequency is tied. Such summaries will be produced for all AEs, serious adverse events (SAEs), grades 3 or 4 AEs, AEs leading to study treatment discontinuation, and AEs leading to dose-adjustment or interruption of any of the drugs of the treatment. All of these summaries will be by system organ class, preferred term, starting dose level if applicable and, in some case, worst grade. Most of the summaries will be produced twice, once for all events regardless of study treatment relationship, and once for events suspected to be study treatment related. All deaths will be listed and summarized. All AEs will be listed, and any other information collected (e.g., start/end dates and duration of adverse event, severity or relatedness to study medication) will be listed as appropriate.

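### SAP 3.4.1 divides actual and planned dose by the same actual duration, so RDI is a dose-completion fraction that ignores delay and PDI is not a planned quantity

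*SAP*

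**What the plan says.** SAP 3.4.1 defines one duration of treatment: last dosing date minus "first date of study drug + 1) / 30.4375", in months. Three metrics follow.

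- ADI is cumulative actual dose divided by that duration.
- PDI is cumulative planned dose divided by "duration of treatment (months), where cumulative planned dose = planned number of S95014 infusions" multiplied by the starting dose.
- RDI is ADI divided by PDI.

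Section 3.4.1 does not give the planned number of infusions, but SAP 2.2 does: "Patients will be administered 9 infusions of S95014 lyophilizate, at week 7, 9, 11, 15, 17, 19, 23, 25 and 27". No planned duration is defined anywhere in the SAP.

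Section 3.4.1 also summarises duration, number of doses and cumulative dose, and plans two listings: "Exposure to S95014 lyophilizate for each subject will be listed" and "Listing of all dose change/interruption and reasons will be produced". Under SAP 3.1.1, quantitative data are summarised by "mean, standard deviation, median, first and third quartiles, minimum and maximum will be presented".

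**The concern.** A reader who sees a relative dose intensity of 100% will take it that dose and timing were both kept, and will take planned dose intensity to be a property of the plan. Neither holds here. Delay is foreseeable, because Protocol 8.10 provides for interruptions and reductions during consolidation. Very early stops are possible too: the same section lists toxicities that end treatment, and the safety set in SAP 2.1 includes anyone with one dose.

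At stake is how the exposure tables read beside the safety results. A line named as an intensity would carry no schedule information. The mean, SD and maximum of ADI and PDI could also be driven by one patient who stopped very early.

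**Working it through.** The documents give no numerical ADI, PDI or RDI to reproduce, so the SAP formulas are applied to the stated schedule.

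**Inputs.** Weeks 7, 9, 11, 15, 17, 19, 23, 25 and 27 (SAP 2.2) put the infusions on days 1, 15, 29, 57, 71, 85, 113, 127 and 141. One month is 30.4375 days (SAP 3.4.1). The starting dose D is 1000 U/m² for illustration; it cancels from each patient's ratios. About 88 patients are planned (Protocol synopsis).

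**Step 1: RDI.** With L the actual duration in months,

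RDI = (cumulative actual dose / L) / (9 × D / L) = cumulative actual dose / (9 × D).

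The cancellation is exact for any pattern of dose, delay or stopping. It also holds if the planned number is read as the number planned up to discontinuation.

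**Step 2: stopping after k on-schedule infusions at constant dose.** ADI = 1000k / (days/30.4375) and PDI = 9000 / (days/30.4375), both in U/m² per month. The last column divides the SAP's ADI by the ADI obtained when 14 days are credited from the last infusion, that is (days + 13) / days. The 14-day credit is an assumption, not a rule in the documents.

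| k | Days | ADI | PDI | PDI vs full course | RDI | ADI vs 14-day credit |
|---|---|---|---|---|---|---|
| 1 | 1 | 30,438 | 273,938 | 141 | 11.1% | 14.0 |
| 2 | 15 | 4,058 | 18,263 | 9.4 | 22.2% | 1.87 |
| 3 | 29 | 3,149 | 9,446 | 4.86 | 33.3% | 1.45 |
| 4 | 57 | 2,136 | 4,806 | 2.47 | 44.4% | 1.23 |
| 5 | 71 | 2,143 | 3,858 | 1.99 | 55.6% | 1.18 |
| 6 | 85 | 2,149 | 3,223 | 1.66 | 66.7% | 1.15 |
| 7 | 113 | 1,886 | 2,424 | 1.25 | 77.8% | 1.12 |
| 8 | 127 | 1,917 | 2,157 | 1.11 | 88.9% | 1.10 |
| 9 | 141 | 1,943 | 1,943 | 1.00 | 100% | 1.09 |

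**Step 3: delay.**

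- Nine full doses with 28 days' total delay last 169 days. RDI is 100% and ADI is 9000 / (169/30.4375) = 1,621.
- With 60 days' delay the course lasts 201 days. RDI is again 100% and ADI is 1,363.
- A patient 28 days late who misses week 27 has 127 + 28 = 155 days. PDI is then 141/155 = 0.91 of the full-course value.

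**Step 4: effect on a mean.** Assume one of n patients stops after one infusion, the rest complete on schedule, and all share one starting dose. Mean ADI rises by (141/9 − 1)/n and mean PDI by (141 − 1)/n. For n = 88 these are 14.667/88 = 16.7% and 140/88 = 159%, so mean PDI becomes 2.59 times its value. Medians and quartiles do not move, because the other 87 values are identical.

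**Step 5: why re-basing PDI alone does not repair RDI.** With PDI fixed at the 141-day value, ADI/PDI is 30,438/1,943 = 15.7 after one infusion. With a 14-day credit in both terms it is (1000/14) / (9000/154) = 1.22, and the same after two or three infusions.

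**The case against.** The strongest reply is that nothing is miscalculated. The formulas are printed, and the quantity called RDI is a legitimate completion measure that responds to omitted and reduced doses. Delay and early stopping also remain visible in duration, number of doses, cumulative dose, ADI and the two listings. Protocol 6.2 requires that "All dosages of S95014 prescribed to the patient and all dose changes during the study must be recorded in the eCRF", and Protocol 6.4 assesses compliance by vial count rather than by RDI. The table templates are in a separate document, so labels and footnotes cannot be checked. All of this stands, and it makes the point one of definition and labelling. It does not make PDI a planned quantity or give RDI any schedule content.

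Four stronger readings are tempting, and the documents do not support them.

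- A reader might infer that ADI is distorted only for stops after one to three infusions, since against the SAP's full-course value its ratios are 15.67, 2.09 and 1.62, then between 0.97 and 1.11. That yardstick of 141 days itself gives the last infusion no interval. Against a 14-day credit, ADI is high at every stopping point.
- A reader might infer that every early stop inflates PDI. That holds for on-schedule dosing only; the 155-day example gives 0.91.
- A reader might take 16.7% as a general figure. It needs a common starting dose. Compared with the same patient completing, a 2500 U/m² patient stopping after one infusion among 1000 U/m² patients raises mean ADI by about 41%; a 1000 among 2500 raises it by about 7%. The documents give no stopping rate or dose mix.
- A reader might infer that the safety results are compromised. The adverse event tables in SAP 3.5.1 count subjects, "presenting the number and percentage of subjects having at least one AE", and do not use these metrics.

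**Conclusion.** The point holds and is minor. That the duration cancels, and that PDI moves with the patient's actual dates, is exact algebra on SAP 3.4.1 and needs no assumption. The PDI multiples assume on-schedule dosing before the stop. The size of the ADI excess depends on the 14-day convention. The effects on means are illustrations under the assumptions in step 4; with no very early stopper, that effect does not arise. The consequence is confined to descriptive exposure tables in a study without a hypothesis test.

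**What to change.** In SAP 3.4.1:

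1. Relabel the current RDI as percent of planned cumulative dose = cumulative actual dose / (9 × starting dose), citing the 9 infusions in SAP 2.2.
2. Stop dividing planned dose by actual duration. Either drop PDI, or compute it from the planned week 7 to week 27 calendar so that it is the same for all patients with the same starting dose. State the convention for planned duration, because it matters: at 1000 U/m², PDI is 1,943 over 141 days, 1,779 over 154 days, and 1,500 over the 6-month treatment period in the Protocol synopsis.
3. Do not report ADI divided by the re-based PDI as RDI, since it exceeds 100% for very early stoppers (step 5).

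Two additions are optional. A stated interval could be credited to the last infusion in ADI, labelled as a convention because the calendar has 28-day steps after weeks 11 and 19. A schedule-sensitive RDI while on treatment could be shown beside item 1, never in its place: it would be 154/182 = 84.6% for nine full doses with 28 days' delay, but 100% for an on-schedule patient who only omits week 27.

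The cost is one derivation change and one or two lines in the table templates. The schedule-sensitive RDI would also need a rule assigning each infusion to its scheduled week, which the SAP lacks.

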3.4.2. Concomitant treatments

Concomitant medication for each subject in the SAS will be listed.

3.5. Safety analysis

All subjects included in the safety analyses will be evaluated overall and by the starting dose level if applicable, unless otherwise specified.

3.5.1. Adverse Events

A treatment-emergent adverse event (TEAE) is defined as any untoward medical occurrence in a subject who received IMP (S95014), which occurs within the period from the Inclusion visit, until 30 days after the last S95014 infusion, or the date of withdrawal, whichever is earlier. TEAE will be assessed according to the National Cancer Institute (NCI) Common Terminology Criteria Adverse Events (CTCAE) v5.0. Clinically significant laboratory abnormalities will be classified into Common Terminology Criteria (CTC) grade according to CTCAE v5.0 and will be reported as adverse events if they are associated with signs and symptoms or, clinically significant in the investigator's opinion except if related to the disease, if they require curative therapies, if they induce change of study treatment administration. All analyses described below will be based on TEAEs, if not otherwise specified.

Adverse events will be summarized in hierarchical tables, presenting the number and percentage of subjects having at least one AE, and having at least one AE in each primary system organ class and for each preferred term using MedDRA coding. AEs will be sorted by descending frequency, and alphabetically where frequency is tied. Such summaries will be produced for all AEs, serious adverse events (SAEs), grades 3 or 4 AEs, AEs leading to study treatment discontinuation, and AEs leading to dose-adjustment or interruption of any of the drugs of the treatment. All of these summaries will be by system organ class, preferred term, starting dose level if applicable and, in some case, worst grade. Most of the summaries will be produced twice, once for all events regardless of study treatment relationship, and once for events suspected to be study treatment related. All deaths will be listed and summarized. All AEs will be listed, and any other information collected (e.g., start/end dates and duration of adverse event, severity or relatedness to study medication) will be listed as appropriate.

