2.2.4. Study rationale and design

A phase II, parallel, open-label study, named CL2-95014-002, was set-up to demonstrate the pharmacokinetic comparability of both liquid and lyophilized S95014 formulations in newly-diagnosed paediatric ALL patients.

The present CL2-95014-003 study is designed to provide continued access to S95014 during the consolidation phase in patients who completed the CL2-95014-002 study and who are clinically benefitting from S95014 without major toxicity.

Patients will be administered lyophilized S95014 during the consolidation phase at the dose of 1000, 2000 or 2500 U/m², as per investigator's judgment. Backbone chemotherapy regimen will be administered as per ALL-MB 2015 protocol.

The study will be conducted in compliance with the protocol, GCP, the ethical principles that have their origin in the Declaration of Helsinki and the applicable regulatory requirements.

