8.9. Reporting procedures

8.9.1. Time frame for AE reporting

Any event meeting the above mentioned definitions (see sections 8.3 to 8.7) must be reported to the sponsor on an adverse event form if it occurred:

- before the first intake of the IMP for events related to the research
- at any time after the administration of IMP, up to the participant's withdrawal visit for all events,
- up to 30 calendar days after the participant's last intake of IMP for all ERIN, regardless of the supposed role of the research.
- irrespective of the time of onset after the end of the study in case of serious adverse event related to the research.

[figure not shown]
Of note, events occurring between the signature of the informed consent and the first administration of the test drug for which the investigator does not consider an association with

¹ Instrumental Activities of Daily Living (ADL) refer to preparing meals, shopping for groceries or clothes, using the telephone, managing money, etc.

² Self-care ADL refer to bathing, dressing and undressing, feeding self, using the toilet, taking medications, and not bedridden”.

any procedure/condition required by the study protocol must be reported as **medical history** or as signs and symptoms related to the studied disease in the dedicated form of the CRF.

For a given patient, medical histories and adverse events already reported in the initial CL2-95014-002 study will not be reported in the eCRF, except in case of worsening.

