1.2.1. Study plan

Written informed consent and assent (when appropriate) will be obtained from each patient and/or his/her parent(s)/legal representative during the inclusion visit, corresponding to the withdrawal visit of the initial CL2-95014-002 study.

S95014 lyophilizate will be administered IV every two weeks during the consolidation phase at the dose of 1000, 2000 or 2500 U/m², as per investigator's judgment. Patients will be administered 9 infusions of S95014 lyophilizate, at weeks 7, 9, 11, 15, 17, 19, 23, 25 and 27. Patients will receive other backbone chemotherapy agents as per ALL-MB 2015 protocol (see study protocol Appendix 1).

The study duration will be approximately 7 months, including the treatment period consisting of the consolidation phase and the follow-up period. After completing the consolidation phase, patient will be discontinued from the study and will be treated as per investigator's judgment.

The study will be divided into the following periods for each participant:

- **Inclusion visit:** to obtain informed consent and check the inclusion/non-inclusion criteria. The inclusion visit of CL2-95014-003 study will correspond to the withdrawal visit of the initial CL2-95014-002 study.
- **Treatment period:** As per ALL-MB 2015 protocol, treatment period will start at Day 1 of the consolidation phase. Patients will be on treatment until the end of the consolidation

[figure not shown]

phase, unless they meet a discontinuation criterion as described in the Clinical Study Protocol.

- **Withdrawal visit:** no later than 30 days after the last dose of S95014 during the consolidation phase. Patient will continue receiving backbone chemotherapeutic regimen as per ALL-MB 2015 protocol, according to physician's judgment.
- **Follow-up visit:** should be made after Withdrawal visit, a contact or telephone call will be done not earlier than 30 days after the last S95014 infusion, except in case of consent withdrawal. Follow-up of adverse events and the patient's survival will be recorded.

The study plan is shown in Figure (1.2.1) 1.

Figure (1.2.1) 1 - Study plan

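### The SAP opens the TEAE window at the inclusion visit, so an adverse event recorded before the first S95014 infusion of this study is tabulated as treatment-emergent under a starting dose not yet given

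*SAP*

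**What the plan says.** SAP 3.5.1 counts as a TEAE any untoward occurrence in a subject who received S95014 "which occurs within the period from the Inclusion visit, until 30 days after the last S95014 infusion", or the withdrawal date if that is earlier. The adverse event analyses use TEAEs unless otherwise specified. SAP 3.5 adds the grouping: "All subjects included in the safety analyses will be evaluated overall and by the starting dose level if applicable, unless otherwise specified".

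SAP 1.2.1 fixes the start of that window: "The inclusion visit of CL2-95014-003 study will correspond to the withdrawal visit of the initial CL2-95014-002 study". It also gives the dosing schedule: "Patients will be administered 9 infusions of S95014 lyophilizate, at weeks 7, 9, 11, 15, 17, 19, 23, 25 and 27". SAP 2.2 names the product: "S95014 lyophilizate is considered as IMP". The secondary objective (SAP 1.1.2) is the safety profile of that lyophilizate in consolidation.

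The induction study was a parallel study set up "to demonstrate the pharmacokinetic comparability of both liquid and lyophilized S95014 formulations in newly-diagnosed paediatric ALL patients".

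On recording, Protocol 8.9.1 sends an event to the adverse event form if it occurred "before the first intake of the IMP for events related to the research". Other events before the first dose go to medical history or disease symptoms. Events already reported in CL2-95014-002 are not entered again unless they worsen. Protocol 3 and SAP 1.1.2 say instead that every adverse event is collected from consent, whatever its cause.

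**The concern.** An event between the inclusion visit and the week-7 infusion precedes all S95014 given in this study. The only S95014 it can follow is the induction dose, which for some children was presumably the liquid formulation. The SAP would still show the event as treatment-emergent on lyophilizate at 1000, 2000 or 2500 U/m².

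Safety description is the only objective this study analyses, and it has no comparator. An event in the wrong period is therefore not offset by a similar error in a control arm. It adds directly to the reported incidence, and proportionally more in a small dose column.

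**Working it through.** The plan attaches no figure to this point, so there is none to reproduce. The check compares definitions and then gives a scale.

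**1. Order of events.** In the Protocol's Table (4.1.2) 1, the inclusion visit is a separate column before W7, with no S95014 given at it. The window therefore contains pre-dose time unless inclusion and the first infusion fall on the same day.

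**2. Other definitions in the SAP.**

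| Place | Reference point |
|---|---|
| SAP 2.1, safety analysis set | at least one dose in this study |
| SAP 3.4.1, duration of treatment | first date of study drug |
| SAP 3.5.2, urinalysis shift tables | after the first infusion |
| SAP 3.1.2, baseline | before the first dose in CL2-95014-002 |
| SAP 3.5.1, TEAE | inclusion visit |

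The inclusion visit is neither the first dose of the induction study nor the first dose of this one. No SAP rule removes or flags pre-dose events. Protocol 10 defines no TEAE window, so SAP 3.5.1 is the only source.

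**3. Which gap events can reach the tables.**
- Under Protocol 8.9.1: worsened CL2-95014-002 events, and new pre-dose events judged related to the research.
- Under Protocol 3 and SAP 1.1.2: any new gap event, whatever its cause.
- Under both: Protocol 5.2.2, criterion 13, keeps out children with a major safety issue from previous S95014.

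**4. Share of the window that is pre-dose.** First to last infusion: (27 − 7) × 7 = 140 days. Adding 30 days gives 170 days at most after the first dose. With a gap of g days the share is g / (g + 170). The documents do not give g, so these values are assumed:

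| g (days) | 0 | 3 | 7 | 14 | 28 |
|---|---|---|---|---|---|
| Share | 0% | 1.7% | 4.0% | 7.6% | 14.1% |

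**5. Effect on an incidence.** One child whose only event in a category is pre-dose adds 1/88 = 1.1 points overall, using the planned 88. In a dose column of 30 or 15 children (assumed sizes) the addition is 1/30 = 3.3 or 1/15 = 6.7 points.

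For illustration, let p be the true on-treatment incidence and q the proportion of children with a counted pre-dose event in the same category, taken as independent. The observed incidence is 1 − (1 − p)(1 − q). With p = 10%:

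| q (assumed) | Expected children, 88q | Observed incidence |
|---|---|---|
| 1% | 0.9 | 10.9% |
| 2% | 1.8 | 11.8% |
| 5% | 4.4 | 14.5% |
| 10% | 8.8 | 19.0% |

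No value of p or q is in the documents. The table shows scale only.

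**The case against.** The best defence has four parts.

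**Controls on entry.** Protocol 8.9.1 bars re-entry of CL2-95014-002 events unless they worsen and sends unrelated pre-dose events to medical history. Criterion 13 removes the children most likely to have serious carry-over. This stands, and it makes the number smaller. It does not make it zero, and the wording in Protocol 3 and SAP 1.1.2 would bypass the routing to medical history.

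**Continuous exposure.** SAP 3.1.2 sets baseline before the first dose in CL2-95014-002, so S95014 exposure could be seen as running through both studies. That would justify a window opening at the induction dose, with the formulation shown. It does not justify one opening at the inclusion visit, and it does not fit columns defined by the starting dose of this study.

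**Limited consequence.** The analysis is descriptive, the dose columns group children without attributing cause, and all adverse events are listed, with dates as appropriate. A careful reader could find a pre-dose onset in the listing. The summary tables would still not show it.

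**Stronger readings are not supported.** A reader might infer that induction carry-over in general is counted, that the pre-dose events are mainly late effects of the induction dose, or that they concentrate in the related-event tables. The first ignores the controls above. The other two are not shown. Under Protocol 8.8, relation to the research also covers procedures, treatment changes and backbone drugs, whereas the second set of tables in SAP 3.5.1 covers only events suspected to be related to study treatment. An event with missing causality would enter those tables, because SAP 3.2 counts it as related, but nothing says how often that would happen.

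**Conclusion.** The definition is wrong as written. It starts before exposure in this study, does not match the objective or the SAP's own analysis-set and exposure definitions, and places any recorded gap event under a dose not yet given.

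The size is unknown and may be small. It depends on the gap between inclusion and week 7, on which collection rule the sites follow, and on whether an affected child has a later event in the same category. One child is at most 1.1 points of 88. The 3.3 to 6.7 points for a dose column rest on assumed column sizes. That some children had received only liquid S95014 by this point is a fair inference from the parallel design of CL2-95014-002, but their number is not given. The change is worth making because it is cheap and removes the ambiguity, not because a large distortion has been shown.

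**What to change.** - In SAP 3.5.1, start the TEAE window at the first S95014 infusion in CL2-95014-003, by date and, where recorded, time. Count a pre-existing event as treatment-emergent if it worsens after that infusion.
- List and count events from consent to that infusion separately, show the formulation received in induction, and keep them out of the starting-dose columns.
- Say how partial onset dates are handled. SAP 3.2 sets a missing day to the first of the month, which could move an event in the month of the first infusion to the pre-dose side.
- Reconcile Protocol 3, Protocol 8.9.1, SAP 1.1.2 and SAP 3.5.1 on which pre-dose events are collected as adverse events.

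The cost is a few sentences of SAP wording, one extra listing with a count, and a clarification of the collection rule. Onset dates and infusion dates are already used in the planned analyses. The induction formulation comes from CL2-95014-002, whose data Protocol 17.1.3 already allows in this study's report.
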